## **10.2.2      *Replacement of Participants Who Withdraw from the Study***

Participants who withdraw from the study after receiving an initial dose of treatment will not be replaced. If a participant withdraws after randomization and before dosing, that participant may be replaced. The replacement participant will undergo the same stratification procedure as a new participant; no special replacement randomization schedule is necessary.

## **11            *EVALUATION, RECORDING, AND REPORTING OF ADVERSE EVENTS***

### **11.1          *Definitions***

#### **11.1.1        *Adverse Event***

An AE is any untoward medical occurrence, or the deterioration of a preexisting medical condition (other than the condition that is being treated by the study) associated with the use of a study medication in humans, whether or not it is considered related to the study medication. An AE (also referred to as an adverse experience) can therefore be any unfavorable and unintended sign (eg, tachycardia, enlarged liver, clinically important or abnormal laboratory result), participant-reported symptom (eg, nausea, chest pain), or evidence of any disease activity temporally associated with the use of a study medication, whether or not related to the study medication.

In clinical studies, an AE can include an undesirable medical condition occurring at any time after the participant has signed informed consent, including run-in or washout periods, even if no specific treatment has been administered.

Preexisting medical conditions (other than natural progression of the disease being studied) judged by the investigator or participant to have worsened in severity or frequency or changed in character during the protocol-specified AE reporting period will be reported as AEs or SAEs as appropriate.

Imaging-based assessments of a decrease in contractility are not considered AEs unless associated with symptoms or signs of clinical concern on the part of the investigator. Such events should be categorized as an AE defined in terms of those symptoms or signs.

An AE or SAE can also be a complication that occurs as a result of protocol-mandated procedures (eg, invasive procedures such as biopsies).

For MyoKardia to collect additional information about clinically important laboratory results or diagnostic tests (eg, blood, ECG, imaging), at a minimum, the following abnormalities should be captured on the AE eCRF:

- Any test result that meets the definition of an SAE
- Any clinically important test abnormality that suggests a disease and/or organ toxicity is worsening or is new (eg,  $>3\times$  deviation from the upper or lower limit of the analyzing laboratory reference range, or as otherwise specified in the protocol)

- Any test abnormality that requires the participant to have study medication discontinued or interrupted or in the clinical judgment of the investigator
- Any test abnormality that requires the participant to receive specific corrective therapy, close observation, more frequent follow-up assessment, or further diagnostic investigation

The term AE is used generally to include any AE whether serious or nonserious.

#### **11.1.1.1 Events Not Meeting the Definition of Adverse Event**

Events that do not meet the definition of AE include the following:

- Any clinically significant abnormal laboratory findings or other abnormal safety assessments that are associated with the underlying disease under study, unless judged by the investigator to be more severe than expected for the participant's condition
- The disease/disorder being studied or expected progression, signs, or symptoms of the disease/disorder being studied, unless more severe than expected for the participant's condition
- Medical or surgical procedure (eg, endoscopy, appendectomy): the condition that led to the procedure is the AE
- Situations in which an untoward medical occurrence did not occur (social and/or convenience admission to a hospital)
- Anticipated day-to-day fluctuations of preexisting disease(s) or condition(s) present or detected at the start of the study that do not worsen
- Hospitalization for a preexisting condition, provided that all of the following criteria are met:
  - The subject has not experienced an AE.
  - The hospitalization was planned prior to the study or was scheduled during the study when elective surgery or procedure became necessary because of the expected normal progression of the disease.

#### **11.1.2 *Serious Adverse Event***

An SAE is an AE that fulfills one or more of the following criteria in the opinion of the investigator or MyoKardia:

- Results in death
- Is immediately life-threatening (places the participant at immediate risk of death from the event as it occurred)
- Requires in-participant hospitalization or prolongation of existing hospitalization

- Results in persistent or significant disability or incapacity or substantial disruption of the ability to conduct normal life functions
- Results in a congenital abnormality or birth defect
- Is an important medical event that may not result in death, be life-threatening, or require hospitalization, but may be considered an SAE when, based upon appropriate medical judgment, it may require medical or surgical intervention to prevent one of the outcomes listed above

## **11.2 Adverse Event Reporting and Descriptions**

### ***11.2.1 Reporting Period and Follow-up***

AEs will be assessed from the time the participant provides informed consent through the duration of the study. Preexisting medical conditions that increase in severity from the first dose of study medication will be reported as AEs. Preexisting medical conditions that increase in severity after providing informed consent but before the first dose of study medication will be reported as medical history.

Any AEs that are unresolved at the participant's last visit in the study are followed by the investigator until resolved or stabilized and are considered irreversible, or the participant has died.

MyoKardia retains the right to request additional information for any participant with ongoing AE(s)/SAE(s) at the end of the study, if judged necessary.

### ***11.2.2 Adverse Event Attributes***

The following attributes will be recorded for each AE. Additional attributes may be collected as required by MyoKardia.

#### **11.2.2.1 Description**

All AEs spontaneously reported by the participant or reported in response to the open question from the study personnel "*Have you had any health problems since you were last asked?*" , or revealed by observation will be collected and recorded in the eCRF.

When collecting AEs, the recording of diagnoses is preferred (when possible) to recording a list of signs and symptoms (eg, anemia, not low hemoglobin). However, if a diagnosis is known and there are other signs or symptoms that are not generally part of the diagnosis, the diagnosis and each sign or symptom will be recorded separately.

Death is an outcome and not the name of the event. In this situation, the event that led to the death is the name of the event. If the cause of death is unknown, "found dead" is an acceptable description.

#### 11.2.2.2 Start Date/Time and Stop Date/Time

The date (and time during the period of residency) that the AE started and the date (and time during the period of residency) that the event ended will be recorded. For events that continue for long periods of time, recording the end date as the day the event stabilized will be acceptable.

#### 11.2.2.3 Relationship to Study Treatment (Suspected Adverse Reactions)

The investigator should assess causality by answering either “yes” or “no” to the question “Is there a reasonable possibility that the event may have been caused by the IMP/study medication?”

#### 11.2.2.4 Intensity

Record the intensity or severity of the event using the following guide:

- Mild (awareness of sign or symptom, but easily tolerated)
- Moderate (discomfort sufficient to cause interference with normal activities)
- Severe (incapacitating, with inability to perform normal activities)
- Life-threatening (urgent intervention indicated)
- Fatal (event led to death)

#### 11.2.2.5 Seriousness

Record SAE criteria described in [Section 11.1.2](#) or indicate that the AE is not serious.

**It is important to distinguish between category (AE vs SAE) and intensity (mild, moderate, or severe) of AEs.**

Severity is a measure of intensity (Section 11.2.2.4), whereas seriousness is defined by the criteria in [Section 11.1.2](#).

An AE of severe intensity need not necessarily be considered serious. For example, nausea that persists for several hours may be considered severe nausea but not an SAE. On the other hand, a stroke that results in only a limited degree of disability may be considered a mild stroke but would be an SAE.

#### 11.2.2.6 Outcome

Record the outcome of the event based on the options provided on the eCRF.

### 11.3 **Reporting and Evaluation of Serious Adverse Events**

All SAEs occurring during the treatment-emergent period (defined as the period from the first administration of study drug to 56 days [5 half-lives] after the last administration of study drug [corresponding to Week 30]) regardless of causality will be reported by the

investigator or designee to MyoKardia/designee within 24 hours of knowledge of the event or sequelae. Deaths and SAEs occurring after the treatment-emergent period and considered related to study medication or study procedure must also be reported. SAE reporting instructions are provided in the Study Reference Manual.

SUSARs are SAEs that qualify for mandatory expedited reporting to regulatory authorities when the SAE is suspected to be caused by the study treatment and is considered unexpected (ie, not defined as expected in the current IB, clinical protocol, or approved labeling for marketed products). In this case, MyoKardia or designee will report to the relevant regulatory authority(ies) and forward a formal notification describing the SUSAR to investigators, according to regulatory requirement. Each investigator must then notify his/her ethics committee (EC) of the SUSAR as required by local regulatory authorities and in accordance with their EC policy.

#### **11.4 Reporting Adverse Events of Special Interest**

Overdose, pregnancy, and LVEF  $\leq 30\%$  as determined by local site read echocardiogram are considered Adverse Events of Special Interest (AESI). If AESI occurs, this must be reported within 24 hours to MyoKardia.

### **12 STATISTICAL METHODS**

#### **12.1 Determination of Sample Size**

Approximately 220 participants will be randomized, with 110 participants in each of the 2 groups. Randomization will be stratified for NYHA functional classification (II or III), current treatment with  $\beta$ -blocker (yes/no), type of ergometer (treadmill or exercise bicycle), and consent for the CMR substudy (yes or no). The sample size should provide adequate power to determine the superiority of mavacamten in improving pVO2 and NYHA functional class relative to placebo (see [Section 12.2.1](#)). The power calculation is derived assuming a true clinically meaningful difference of 25% between mavacamten and placebo participants in achieving the clinical response. Based on the MYK-461-004 PIONEER-HCM phase 2 study, 50% of the participants receiving mavacamten met the clinical responder definition by the end of 12-week treatment period. Assuming the same percentage of participants in the active treatment arm and 25% in placebo arm will achieve the clinical response at the end of 30-week dosing period in the current study, the proposed sample size of 110 participants per arm will provide 96% power at two-sided 5% statistical significance level. Participants who terminate early or cannot be assessed for the clinical response at the end of 30-week dosing period will be considered as non-responders.

#### **12.2 Study Endpoints**

[figure not shown]
The study design is a randomized two-arm double-blinded trial, and the conceptual analytical approach is to compare the mavacamten treatment arm with the placebo arm.

### ***12.2.1 Primary Efficacy Endpoints***

- Clinical response defined as achieving: 1) An improvement of at least 1.5 mL/kg/min in peak oxygen consumption (pVO2) as determined by CPET and a reduction of one or more class in NYHA Functional Classification *or* 2) an improvement of 3.0 mL/kg/min or more in pVO2 with no worsening in NYHA Functional Class.

### ***12.2.2 Secondary Efficacy Endpoints***

- Change from baseline to Week 30 in post-exercise LVOT peak gradient
- Proportion of participants with at least 1 class improvement in NYHA functional class from baseline to Week 30
- Change from baseline to Week 30 in pVO2 as determined by CPET
- Change from baseline to Week 30 in participant-reported health-related quality of life as assessed by the KCCQ score
- Change from baseline to Week 30 in patient-reported severity of HCM symptoms as assessed by the HCMSQ score

## 12.2.5 Safety Endpoints

- Incidence of major adverse cardiac events (death, stroke, acute myocardial infarction)
- Incidence of hospitalizations (both cardiovascular (CV) and non-CV))
- Incidence of heart failure (HF) events, (includes HF hospitalizations and urgent emergency room (ER)/outpatient (OP) visits for HF)
- Incidence of atrial fibrillation/flutter (new from screening)
- Incidence of ICD therapy and resuscitated cardiac arrest
- Incidence of Ventricular tachyarrhythmias (includes VT, VF, and Torsades de Pointe)
- Incidence of syncope and seizures
- Frequency and severity of treatment-emergent adverse events (TEAE), treatment-emergent SAEs, and laboratory abnormalities (including trends in NT-proBNP)

## 12.4 Statistical Analysis

Before database lock, final SAPs for clinical data and PK data will be prepared that contain full details of all planned analyses. The analyses presented here represent an outline of the intended methodology.

#### ***12.4.1 Analysis Populations***

Six analysis populations are defined in this study:

- Intention-to-treat (ITT) Population: all randomized participants regardless of whether they receive study drug, with analyses conducted according to the randomized treatment assignment
- Per Protocol Population: all randomized participants who reached Week 30 visit and completed all efficacy assessments, with analyses conducted by actual treatment received
- Safety Analysis Population: all randomized participants who receive at least 1 dose of study drug, with analyses conducted by actual treatment received
- PK Analysis Population: all randomized participants who receive at least 1 dose of study drug [REDACTED]

[REDACTED]

[REDACTED]

[REDACTED]

[REDACTED]

#### ***12.4.2 General Considerations***

Descriptive summary statistics for continuous variables will include the number of participants, mean, standard deviation (SD) or standard error, median, minimum, and maximum. Nominal categorical variables will be summarized using counts and percentages. Ordinal variables may be analyzed as continuous variables as if they were continuously scaled.

#### ***12.4.3 Participant Disposition***

The number and percentage of participants who complete and discontinue as well as reasons for early discontinuation will be presented.

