## **7 STUDY TREATMENT**

Study drug is defined as mavacamten (MYK-461) or placebo.

All randomized study participants will receive either mavacamten or placebo in a double-blinded manner.

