### 7.3.2 *Blinded Dose Adjustment Leading to Temporary Discontinuation*

In addition to the blinded dose adjustments described above (which are not preceded by dose discontinuation), at any time (T) during the treatment period, dosing may be temporarily discontinued in the case of exaggerated pharmacologic effect (systolic dysfunction), higher than expected plasma concentration, or excessive QTcF prolongation as described below.

If participant has a resting LVEF <50%, plasma drug concentration  $\geq$ 1000 ng/mL, or QTcF stopping criteria described below, as determined by the echocardiography central laboratory, PK analysis laboratory, or ECG core laboratory, respectively, it will be communicated to the investigator and Sponsor that a criterion for temporary discontinuation has been met. Upon receipt of this information, the study site/investigator will contact the participant by telephone and instruct the participant to discontinue study drug and to return for an onsite visit within 2 to 4 weeks (T+2 to 4 weeks). This could correspond to a scheduled or unscheduled visit. Note that to avoid potential bias the IXRS will randomly select participant(s) from the placebo arm to undergo an unscheduled follow-up visit (see also Section 6.2).

Criteria for temporary discontinuation due to QTcF prolongation are as follows and depend on QRS width as determined by the ECG core laboratory:

- If QRS is narrow ( $<120$  ms), then temporary discontinuation criteria are the smaller of: a 15% increase from baseline QTcF OR QTcF  $\geq 520$  ms
- If QRS is wide ( $\geq 120$  ms), then temporary discontinuation criteria are the smaller of: a 15% increase from baseline QTcF OR QTcF  $\geq 550$  ms

At the follow-up visit (T+2 to 4 weeks), ECG, plasma PK, and TTE will be repeated and another unscheduled visit will be planned for 2 weeks later (T+4 to 6 weeks). If LVEF  $\geq 50\%$  AND plasma drug concentration  $<1000$  ng/mL AND QTcF duration is below programmed discontinuation rules, then the study drug will be restarted at a lower dose (at T+6 weeks) for remainder of the study as follows (previous dose  $\rightarrow$  restart dose):

- Placebo  $\rightarrow$  placebo
- 2.5 mg  $\rightarrow$  placebo
- 5 mg  $\rightarrow$  2.5 mg
- 10 mg  $\rightarrow$  5 mg
- 15 mg  $\rightarrow$  10 mg

If LVEF, plasma drug concentration and/or QTcF persist out of range at the follow-up visit, then study drug will be switched permanently to placebo.

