### **10.1 Treatment Discontinuation**

#### ***10.1.1 Temporary Treatment Discontinuation***

Temporary treatment discontinuation

- Will be implemented when a predefined safety threshold has been met (see [Section 7.3.2](#))
- May be considered by the investigator in the case of an AE/SAE or for another reason

As a general rule, any discontinuation of study drug should be initially considered temporary unless permanent treatment discontinuation is mandated by the protocol (see [Section 10.1.3](#)).

If a temporary treatment discontinuation was caused by a safety threshold being met, blinded treatment will be resumed approximately 4 to 6 weeks later, either at a lower dose or with permanent switch to placebo, transmitted via IXRS (see [Section 7.3.2](#)).

In the case of discontinuation for an AE/SAE, the investigator should make a best effort to resume study drug as soon as practically possible, assuming there are no safety concerns (ie, the investigator is satisfied that in his or her medical judgment, the study drug is unlikely to be responsible for the event concerned).

All temporary treatment interruptions should be recorded in the eCRF.

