#### 12.4.8.1 Adverse Events

AEs will be mapped to system organ classes and preferred terms (PTs) using the Medical Dictionary for Regulatory Activities (MedDRA). AEs will be monitored during the study and the data analyzed with respect to overall incidence as well as severity and potential relationship of AEs to study medication. AEs with onset during the treatment-emergent period, or with an onset before the first dose of study medication that increases in severity or becomes serious during the treatment-emergent period, will be considered treatment-emergent.

Adverse event incidence tables will present the number and percentage of participants experiencing at least one TEAE by system organ class (SOC) (sorted by internationally agreed order), high-level group term (HLGT), high-level term (HLT) and PT in alphabetical order for each treatment group. Multiple occurrences of the same event in the same

participant will be counted only once in the tables within a treatment phase. The denominator for computation of percentages is the safety population within each treatment group.

Adverse event incidence tables will be provided by treatment group for all types of TEAEs: all TEAEs, all treatment-emergent SAEs and all TEAEs leading to permanent treatment discontinuation.

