7. SUBJECT DISPOSITION

The number and percentage of subjects who complete and who prematurely discontinue study drug or study, as well as the reasons for premature discontinuation, will be summarized by randomized treatment assignment for the ITT Population. The reason for screen failure will be summarized for all screened subjects.

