10.6. Other Safety Analysis

Listing of patients with ICD therapy (shock) and appropriateness of therapy as per event adjudication will be provided.

Abnormal physical examination results will be listed by subject and clinical significance.

The number of subjects who met treatment discontinuation criteria per protocol, as well as who met each temporary study drug interruption, will be summarized by treatment and criteria met.

[REDACTED]

[figure not shown]

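### By the plan's own definitions, a mavacamten participant switched permanently to blinded placebo has not discontinued study drug, and no visible table separates these participants from those who resumed mavacamten

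*Protocol*

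**What the plan says.** **Disposition.** Protocol 12.4.3: "The number and percentage of participants who complete and discontinue as well as reasons for early discontinuation will be presented". SAP 7 is more specific and summarises, by randomized arm in the ITT population: "The number and percentage of subjects who complete and who prematurely discontinue study drug or study".

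**Adverse events.** Protocol 12.4.8.1 plans incidence tables for "all TEAEs, all treatment-emergent SAEs and all TEAEs leading to permanent treatment discontinuation". SAP 10.1 keeps the table of events leading to permanent treatment discontinuation. Events leading to an interruption appear there only in by-subject listings.

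**What counts as treatment.** Protocol Section 7: "Study drug is defined as mavacamten (MYK-461) or placebo".

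**The switch.** Protocol 7.3.2 provides for a temporary hold for low LVEF, high plasma concentration or QTcF prolongation. It continues: "If LVEF, plasma drug concentration and/or QTcF persist out of range at the follow-up visit, then study drug will be switched permanently to placebo". The same section gives a second route: a participant who was on 2.5 mg and has come back into range restarts on placebo. Protocol 10.1.1 places all of this under temporary discontinuation: "blinded treatment will be resumed approximately 4 to 6 weeks later, either at a lower dose or with permanent switch to placebo". The eight reasons for permanent treatment discontinuation in Protocol 10.1.3 do not include the switch.

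**Related outputs.** SAP 10.6 counts participants who met the protocol's discontinuation criteria, "as well as who met each temporary study drug interruption, will be summarized by treatment and criteria met". SAP 7.2 lists actual and expected dose adjustments by subject.

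**The concern.** A reader of a disposition table wants to know what share of the mavacamten arm had to come off mavacamten for good, and why. Here a participant can be taken off the active drug permanently, on one of the trial's own safety thresholds, and still be on study drug as the Protocol defines it. The event then sits among interruptions, together with participants who went back to mavacamten at a lower dose.

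The gap can open in one arm only. A placebo participant who is held and restarted goes from placebo to placebo, so nothing is lost from that arm's count. Any omission therefore favours mavacamten on a main tolerability figure.

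**Working it through.** The plan states no figure on this point, so there is none to reproduce. The check is a trace of definitions followed by one division.

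**Trace for a mavacamten participant who is held, switched permanently to placebo, and takes capsules to Week 30**

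1. *Has the participant stopped study drug?* No. Study drug is mavacamten or placebo (Protocol Section 7), and the participant is still taking capsules.
2. *Is the switch a permanent treatment discontinuation?* No. Protocol 10.1.1 classes it as temporary, with treatment resumed, and it is not on the list in 10.1.3.
3. *Row in SAP 7?* Neither study drug nor the study was left early, so the participant counts as not having discontinued.
4. *In the table of TEAEs leading to permanent treatment discontinuation?* Not through the switch, given step 2. A related TEAE would appear in the SAP 10.1 listing of events leading to interruption.
5. *In SAP 10.6?* Yes, as having met an interruption criterion, by arm and criterion. A participant who resumed mavacamten at a lower dose falls in the same row. The other part of that summary, on discontinuation criteria per protocol, points most naturally to 10.1.3, which omits the switch.
6. *In SAP 7.2?* Yes, as a line in a by-subject listing, with no count.

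The trigger is therefore tabulated. Its permanent outcome is not.

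**Size**

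Input: 110 participants per arm (Protocol 12.1, SAP 5). Let D be the participants in the mavacamten arm counted as discontinuing study drug. Let S be those switched for good to placebo who are not already in D.

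- Share shown as having discontinued: D/110
- Share who permanently ceased mavacamten: (D + S)/110
- Gap: S/110

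The documents give no value for S. The values below are assumptions that show the scale.

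| S (assumed) | Gap = S/110, percentage points |
|---|---|
| 0 | 0 |
| 1 | 0.9 |
| 3 | 2.7 |
| 5 | 4.5 |
| 8 | 7.3 |

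The gap in percentage points does not depend on D. The relative understatement, S/(D + S), does, and D is not given either.

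**The case against.** The case that this is minor has several parts.

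- **The safety triggers are reported.** SAP 10.6 counts them by arm and criterion, SAP 10.1 lists TEAEs leading to interruption or discontinuation, and SAP 7.2 lists dose adjustments and flags inconsistencies. This stands. A reader might infer that the plan records nothing but the stopping of study drug, or that it hides the safety signal. The documents do not support that: SAP 7 also counts leaving the study, and only the permanence of the switch lacks a count.
- **The site has a route to record a permanent stop.** Under Protocol 10.1.2 the investigator may treat a discontinuation as permanent when a safety concern has not resolved, and this goes in the eCRF. The investigator is also told that a hold criterion was met (7.3.2). So it would be too strong to say that sites cannot record these withdrawals. Some persistent cases may end as conventional discontinuations and be counted. The rest restart under blind through the IXRS, and the site cannot tell a lower dose from placebo.
- **There may be little to add to the adverse event table.** Protocol 11.1.1 does not treat an imaging-based fall in contractility as an adverse event unless there are symptoms or signs of concern, although it also asks for test abnormalities that force an interruption to be captured. Many switches may therefore have no clinical TEAE. This stands, and it limits that part of the fix to TEAEs already recorded as leading to the hold.
- **Coding is inferred.** Protocol 12.4.3 does not mention study drug, and neither document says how a switched participant is classified for disposition. Parts of the SAP are blacked out and could address it. The sections where the rule would belong (SAP 7, 7.2, 10.1, 10.6) can be read and do not.
- **Safety analysis is descriptive.** The primary endpoint, power and type I error are untouched. This stands, and it is why this is a reporting gap and no more.

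**Conclusion.** The point holds as a gap in reporting. Under the stated definitions, each mavacamten participant switched for good to blinded placebo who continues capsules to Week 30 is left out of the SAP 7 count of study drug discontinuations. No visible table shows these participants as a group. Each is 0.9 percentage points of a 110-participant arm, and the omission can occur only in the mavacamten arm.

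A reader might go further and conclude that the mavacamten discontinuation rate *is* understated, or put a relative size on it. The documents do not support either step. They give neither an expected number of switches nor an expected number of conventional discontinuations, and with no switches the understatement is nil. The route through 2.5 mg may be rare: the modelling in Protocol 7.3.1.1 expects under 1% to reach target concentrations on that dose, although this is not a rate of switching.

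The conclusion rests on two assumptions: that disposition is coded by the Protocol's definition of study drug, and that the blacked-out text contains no contrary rule.

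**What to change.** Change the SAP only, before unblinding. Protocol 12.4 describes its analyses as an outline and leaves the detail to the SAP, so no Protocol text needs to change. No dosing or stopping rule changes.

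1. From IXRS dispensing data, derive one flag for participants randomized to mavacamten whose last change of supply was a permanent switch to placebo after a safety hold.
2. In SAP 7 and 10.6, add a row *mavacamten permanently withdrawn by blinded switch to placebo*, by arm and by the trigger of the hold (LVEF, concentration, QTcF). State in a footnote that the placebo column is zero by construction.
3. Add a total row, *any permanent cessation of mavacamten*, combining the switches with conventional permanent discontinuations and counting each participant once. Keep the existing study drug row, which remains the like-for-like comparison between arms.
4. In SAP 10.1, where a TEAE was recorded as leading to the hold that preceded a switch, show it alongside the TEAEs leading to permanent treatment discontinuation. This uses the link already recorded for the interruption and asks nothing new of blinded sites.

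The cost is one derived flag and a few table rows, from dispensing data the IXRS already holds. If any switch occurs, the mavacamten discontinuation figure becomes slightly less favourable.
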